## **Effect of Cervical Collar on the Optic Nerve Sheath Diameter in Minor Head Trauma**

**NCT03742427**

**13.09.2018**

### **Study Protocol**

Patients appealed to emergency department with blunt head trauma patients, aged >18, Glasgow Coma Score >13 and who signed written informed consent to participate in this study were included. Subjects with known eye or intracranial disease were excluded. All the patients trauma etiology were recorded and were assessed for NEXUS Head Computerized Tomography (CT) Rules for CT scan and the sonographers were blinded for CT examination decision and results.

Patients were lied on a stretcher in a supine position and were told to close their eyes. Sterile ultrasound gel applied to each eyelid of the patients. After gel appliance, 7.5 MHz linear probe with the ophthalmic setting (Mindray M5, Mindray, P.R.C.) was performed to measure the ONSD. The two experienced sonographers each performed at least 350 US per annum. They were certified for basic and advanced emergency sonography by the national emergency medicine society. The intraclass correlation coefficient of the two sonographers for sonographic measurement of ONSD was >0.9 according to local annual quality checks. Both sonographers measured 25 sonographic ONSD each, before this study. Both physicians were blinded to each other measurements. Ultrasound was performed individually in both sagittal and transverse planes. ONSD measurements were taken from the acknowledged standard location 3 mm posterior of the retina. Each eyes measurements were recorded for two times and then a mean binocular ONSD was calculated. In this way, baseline measurements were recorded.

After this baseline measurement, a rigid c-collar (ENPLUS, EN2050, Turkey) was placed for individual patient according to the appropriate size.

The same technique used to measure the ONSD after c-collar placement and the mean ONSD was again calculated. This process was done at time points after placement of c-collar; 5 minutes and 20 minutes. There was only one patient in the ultrasonography room and one researcher in the room at the same time. In this way, both researchers were blinded to each other's measurements.

We reported continuous variables as means and standard deviations (SD) with 95% confidence intervals (CI) since normality in distribution was observed by The Kolmogorov-Smirnov test. The significance of the difference between groups was assessed by ANOVA test. Categorical variables were reported as proportions and counts, and chi-squared test was used to compare proportions among groups. Student's t-test was used as the post-hoc test for ANOVA test, and significance threshold was accepted as  $p < 0.0016$  after Bonferroni correction. The inter-rater reliability of the sonographers for all time points were reported as interclass correlation values and 95% CI.

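### Does having the two sonographers scan one after the other spoil the inter-rater ICCs taken under the collar?

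*Combined protocol and SAP*

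**What the plan says.** The Study Protocol section sets the room rule and gives its purpose as blinding between readers: "There was only one patient in the ultrasonography room and one researcher in the room at the same time", followed by "In this way, both researchers were blinded to each other's measurements".

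The sequence of measurements is a collar-free baseline, then the collar ("After this baseline measurement, a rigid c-collar (ENPLUS, EN2050, Turkey) was placed for individual patient according to the appropriate size"), then repeat scans: "This process was done at time points after placement of c-collar; 5 minutes and 20 minutes". Each post-collar point has one nominal time, not one per reader. On the work in each set, the plan says "Ultrasound was performed individually in both sagittal and transverse planes" and "Each eyes measurements were recorded for two times and then a mean binocular ONSD was calculated".

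On reliability, the closing statistical paragraph says "The inter-rater reliability of the sonographers for all time points were reported as interclass correlation values and 95% CI". The only reliability figure is a pre-study one: "The intraclass correlation coefficient of the two sonographers for sonographic measurement of ONSD was >0.9 according to local annual quality checks".

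The plan does not say who scans first, whether that order is fixed, whether clock times are recorded, or which ICC is meant (model, agreement or consistency, single or average measure).

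**The concern.** An inter-rater ICC needs both sonographers to measure the same patients. With one researcher in the room at a time, they must do so in sequence. That is an inference, since the plan does not say it, but no other reading yields the planned statistic.

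Collar time is the exposure under study. If ONSD rises while the collar is on, the second reader measures a slightly different quantity from the first. Under fixed order, an absolute-agreement ICC falls by the same amount for a collar-time shift as for a reader bias of equal size, and a bias of opposite sign could hide the shift. If order varies and is not logged, both forms of ICC fall. The post-collar ICCs are the trial's evidence that ONSD is measured reliably with the collar on, so a low value could be misread as poor reader agreement.

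**Working it through.** **Inputs from the Study Protocol section.** Two readers, one in the room at a time; two eyes, each recorded twice; two planes; nominal times of 5 and 20 minutes; pre-study ICC above 0.9. That ICC cannot be reproduced, because no data, variance components or ICC form are given. It serves here only as a no-drift reference of 0.90.

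**Assumptions (not in the documents).** 20–30 s per reading; a linear rise of 0.1, 0.2 or 0.3 mm between 5 and 20 minutes; total SD 0.3–0.5 mm; n = 50–200.

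**1. Lag between readers.** A set has 2 × 2 = 4 readings, or 8 if both recordings are made in both planes. The lag is 4 × 20 s = 1.33 min to 8 × 30 s = 4.0 min.

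**2. Shift and fixed-order ICC.** The shift is d = rise × lag / 15. The absolute-agreement ICC is 0.9·SD² / (SD² + d²/2).

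| Rise over 15 min | d (mm) | Absolute-agreement ICC |
|---|---|---|
| 0 | 0 | 0.900 |
| 0.1 mm | 0.009–0.027 | 0.896–0.900 |
| 0.2 mm | 0.018–0.053 | 0.886–0.899 |
| 0.3 mm | 0.027–0.080 | 0.869–0.899 |

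The lowest value is 0.081 / (0.09 + 0.0032) = 0.869, at SD 0.3 and d 0.080. A consistency ICC ignores a constant shift and stays at 0.900 throughout.

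**3. Order varying evenly between patients, no order term.** Either form equals (0.9·SD² − d²/4) / (SD² + d²/4). At SD 0.3 this is 0.885 for d 0.053 and 0.867 for d 0.080.

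**4. Sampling error.** The 95% half-width of an ICC of 0.9 is about 1.96 × (1 − 0.9²) / √(n − 1) = 1.96 × 0.19 / √(n − 1), which is 0.053 at n = 50 and 0.026 at n = 200. The largest fixed-order loss, 0.900 − 0.869 = 0.031, is inside the first and just outside the second.

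**5. What a serious loss would need.** A shift of 0.5 between-patient SD would bring the agreement ICC to 0.809. At total SD 0.3 the between-patient SD is √0.9 × 0.3 = 0.285 mm, so d would have to be 0.142 mm. At the longest lag this implies a rise of 0.142 × 15 / 4 = 0.53 mm over 15 minutes, well above the range considered.

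**6. The comparison over time.** If the first set starts at the nominal time and the readers are averaged, the two set midpoints fall half a lag and one and a half lags later, one lag later on average. Contrasts with baseline then shift by d, that is 0.009–0.080 mm: the nominal 5-minute value describes about 6.3 to 9 minutes. The 5- and 20-minute values shift equally under linearity, so their contrast does not move. With no rise, d = 0, so the lag cannot create an effect that is not there.

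**The case for a change.** The best case for a change is that it costs almost nothing. An order list and one time field need no extra scans, staff or patients, and if order and times are not logged they may be impossible to recover. The ICC form matters too: under fixed order one form absorbs the shift and the other does not.

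The collar-free baseline offers a partial safeguard, since the change in mean reader difference from baseline recovers d. This works only if order is fixed and reader bias is constant. In a simulation with one reader second in 75% of patients and order unrecorded, the apparent reader difference was only 0.027 mm of a true shift of 0.053 mm, with ICCs of 0.885 (agreement) and 0.889 (consistency). The plan does not secure the conditions for the safeguard.

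The omissions and the mechanism stand. The gain from a change is not shown, for three reasons.

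- Silence in a very short protocol, written in the past tense, does not show that order and times went unrecorded. If scanning was complete, a new order rule could not be applied.
- The obvious design remedy is not clearly better. Alternating the order lowers a consistency ICC from 0.900 to 0.885 (SD 0.3, d 0.053) unless an order term is added. Fixed order with a consistency ICC already gives 0.900.
- If the shift varies between patients with SD 0.053 mm, fixed order with a consistency ICC and alternation with an order term both give 0.886.

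**Conclusion.** No change to the plan is called for. Sequential scanning is a sensible price for keeping the readers blind to each other, and the unstated ICC form is ordinary detail that an analyst fills in when reporting. Run as written, the trial keeps its baseline ICC and its main comparison over time. It could lose about 0.00–0.03 from a secondary quality-control ICC at two time points, mostly within that ICC's sampling error.

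These sizes rest wholly on the assumed lag, linear rise, SD and n. With no rise the effect is nil, and a material loss needs a much steeper rise than the range examined. Contrasts with baseline may refer to times a few minutes later than their labels, which bears on how those values are described and not on whether a collar effect is detected. A reader of the results should ask which ICC was used and how the mean reader difference behaved at baseline, 5 and 20 minutes. That is a reporting courtesy, and no conclusion of the trial has been shown to depend on it.

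### One cohort is measured three times, but the plan compares undefined groups by ANOVA and Student's t-test and names no paired or repeated-measures method

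*Combined protocol and SAP*

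**What the plan says.** The Study Protocol section describes one cohort. ONSD is measured in every patient at baseline, a rigid collar is fitted, and the measurement is repeated: "The same technique used to measure the ONSD after c-collar placement and the mean ONSD was again calculated". The timing is given as "This process was done at time points after placement of c-collar; 5 minutes and 20 minutes". With baseline, that makes three measurements per patient. No separate or randomised comparison group appears.

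The value for each occasion is averaged over eyes: "Each eyes measurements were recorded for two times and then a mean binocular ONSD was calculated". Two sonographers take part, and "Both physicians were blinded to each other measurements". No averaging over sonographers is described.

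The closing statistical paragraph, which has no heading of its own, then states:

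- "The significance of the difference between groups was assessed by ANOVA test"
- Student's "t-test was used as the post-hoc test for ANOVA test", at a Bonferroni threshold of p < 0.0016
- "chi-squared test was used to compare proportions among groups"
- "The inter-rater reliability of the sonographers for all time points were reported as interclass correlation values and 95% CI"

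The paragraph does not say what the groups are. Neither it nor the procedures text mentions a paired test, repeated measures, a within-subject effect or a mixed model. It offers 95% confidence intervals for continuous variables but names none for the within-patient change.

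**The concern.** The study asks whether ONSD changes in the same person once a collar is on. That is a within-patient question, but the analysis is worded as a comparison between groups. For the ANOVA, the most plausible groups are the three time points. Followed as worded, independent-group tests would then be applied to correlated data, and between-patient variation in ONSD would stay in the error term although the design allows it to be removed.

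Two consequences follow, in opposite directions:

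- **One value per patient per time point.** With positive between-time correlation, independent-group tests are conservative. A real change can be missed, and a non-significant result can be misread as no effect of the collar.
- **Both sonographers' readings entered as separate independent observations.** The apparent sample size doubles, and type I error can exceed its nominal level when the between-time correlation is low.

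A reader cannot tell which situation applies, nor which test produced the p-values for the main question.

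**Working it through.** **Inputs from the documents.** Three time points per patient; two sonographers; post-hoc threshold 0.0016; between-sonographer intraclass correlation above 0.9. That last figure is agreement between raters on the same occasion, not correlation over time, so it is not used as r.

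**Assumed inputs.** Sample size n, SD, effect and between-time correlation r are not stated. I take SD = 1 at each time point, equal correlation r between any two times, a shift of d SD at both later times, and two-sided tests. An overall alpha of 5% is also assumed.

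**The plan's own figure.** Three pairwise contrasts at 5% give 0.05/3 = 0.0167, not 0.0016. Only 31 or 32 comparisons round to 0.0016 (0.05/31 = 0.00161; 0.05/32 = 0.00156). The threshold is therefore not reproduced, and results are shown at both values.

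**Why the independent test is conservative.** For a difference between two time points:

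- variance assumed by the independent test: 2/n
- true variance: 2(1 − r)/n

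The true variance is (1 − r) times the assumed one. Example with n = 50, r = 0.5, d = 0.3, alpha 0.0016 (critical z = 3.156):

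- assumed SE = √(2/50) = 0.200; true SE = √(2 × 0.5/50) = 0.141
- independent test: the difference must exceed 3.156 × 0.200 = 0.631; (0.631 − 0.3)/0.141 = 2.34, so power is about 1%
- paired test: 0.3/0.141 = 2.12; 2.12 − 3.156 = −1.03, so power is about 15% (12.5% with the exact t-test)

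**Simulation with F and t tests** (200,000 runs, n = 50). Each cell is independent-group / within-patient rejection rate in per cent. The t columns are baseline against 20 minutes.

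| r | ANOVA 5%, d = 0 | ANOVA 5%, d = 0.3 | t at 0.05/3, d = 0.3 | t at 0.0016, d = 0.3 | ANOVA 5%, d = 0.6 | t at 0.05/3, d = 0.6 | t at 0.0016, d = 0.6 |
|---|---|---|---|---|---|---|---|
| 0.3 | 1.5 / 5.0 | 25.5 / 43.0 | 14.0 / 25.8 | 2.4 / 7.3 | 90.5 / 96.3 | 74.7 / 86.1 | 39.1 / 59.7 |
| 0.5 | 0.3 / 5.0 | 20.0 / 56.9 | 10.3 / 36.7 | 1.0 / 12.5 | 93.1 / 99.4 | 78.2 / 95.7 | 37.5 / 80.7 |
| 0.7 | 0.02 / 5.0 | 13.0 / 80.3 | 5.7 / 60.4 | 0.2 / 28.9 | 96.3 / 100 | 83.5 / 99.8 | 35.5 / 97.9 |
| 0.8 | 0.0 / 5.0 | 8.5 / 93.9 | 3.2 / 80.6 | 0.05 / 51.3 | 98.1 / 100 | 87.4 / 100 | 33.4 / 99.9 |

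Other sample sizes at r = 0.5 and d = 0.6:

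- n = 30: ANOVA 65.5 / 92.1; t at 0.0016, 10.7 / 43.8
- n = 100: ANOVA 100 / 100; t at 0.0016, 92.5 / 99.7

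**Stacked readings.** Assume between-sonographer agreement of 0.9. Split the variance into patient (r), patient-by-time (0.9 − r) and reading error (0.1). With 2n rows per time point:

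- variance assumed for a difference: 2/(2n) = 1/n
- true variance: 2[(0.9 − r) + 0.1/2]/n = 2(0.95 − r)/n

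The assumed variance is too small when 2(0.95 − r) > 1, that is, when r < 0.45. Simulated type I error of the 5% ANOVA (n = 50, 60,000 runs) is 14.3%, 10.2%, 5.3%, 4.0% and 0.4% at r = 0.2, 0.3, 0.45, 0.5 and 0.7. A repeated-measures ANOVA on averaged readings stays between 4.9% and 5.1%.

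**The case against.** The strongest reply is that this is loose wording, not a wrong analysis. ANOVA and Student's t-test are family names; nothing says one-way or unpaired, and the within-patient forms may have been used. That stands as a possibility, which is why every consequence here is conditional. But comparing groups is the language of independent samples, and a plan has to identify its test. If the ANOVA groups were patient subgroups instead, no test of change over time would be specified at all. For the chi-squared test, subgroups may well be meant, and an independent-group test would then be correct.

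Second, a conservative test protects a significant result. That is true, but only with one value per patient per time point, which the plan does not guarantee.

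Third, the largest losses at 0.6 SD depend on the 0.0016 threshold, which is itself unexplained. This is fair: at n = 50 the 5% ANOVA loses at most about 6 percentage points for a 0.6 SD shift, and at n = 100 with r = 0.5 it loses nothing. The loss does not vanish without that threshold, however: for 0.3 SD at n = 50 and r = 0.5, ANOVA power is 20% against 57%, and post-hoc power at 0.05/3 is 10% against 37%.

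Fourth, all design inputs are assumed, and no text says that readings were stacked. Inflation would need r below about 0.45, which in this model means that at least 45% of the variance is patient-by-time fluctuation over some 20 minutes; the documents neither support nor exclude that. Stacking is therefore a risk left open by silence, not something the plan states.

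**Conclusion.** The concern holds as a conditional statement and should be resolved before the results are relied on. The design is within-patient, the analysis is worded as between-group, and the only tests described for the main question cannot be identified or reproduced from the text. The documents do not prove that independent-group tests were run.

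If they were, with one value per patient per time point and positive r, the direction of error follows from the algebra. Its size depends on the assumed n, r and effect. The loss is large for small changes or small samples, and small for the overall ANOVA at 0.6 SD with n = 50 or more. At n = 50 and the stated 0.0016, post-hoc power for 0.6 SD ranges from 39% against 60% (r = 0.3) to 33% against 99.9% (r = 0.8). If both sonographers' readings were stacked, the error can run the other way at low r.

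**What to change.** - Define the groups for each test, separating comparisons over time from any comparison of patient subgroups.
- Average the two sonographers' readings to one mean binocular ONSD per patient per time point, or model sonographer within patient.
- For the time comparison, name a repeated-measures ANOVA, or a linear mixed model with a random patient effect and time (baseline, 5, 20 minutes) as a fixed effect. Use paired t-tests for the time contrasts.
- State the number of contrasts behind the Bonferroni threshold.
- Report the mean within-patient change at 5 and at 20 minutes, each with a 95% confidence interval, as the main result.

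If within-patient tests were already used, the cost is a wording correction that says so and states how the two readings entered. If independent-group tests were used, the analysis must be re-run on the same measurements. Neither case needs new data.

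### The post-hoc Bonferroni cutoff of 0.0016 does not follow from the design described: three time-point comparisons at an assumed 5% give 0.0167, and neither alpha nor the number of tests is stated

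*Combined protocol and SAP*

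**What the plan says.** All the relevant text is in the single Study Protocol section of the combined protocol and SAP, including its closing statistical paragraph, which has no heading of its own.

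- **Omnibus test.** "The significance of the difference between groups was assessed by ANOVA test". The word *groups* is not defined.
- **Post-hoc test.** A Student's "t-test was used as the post-hoc test for ANOVA test", and the "significance threshold was accepted as $p < 0.0016$ after Bonferroni correction".
- **Measurement times.** After a baseline scan without the collar, "This process was done at time points after placement of c-collar; 5 minutes and 20 minutes". That makes three time points.
- **Measured variable.** "Each eyes measurements were recorded for two times and then a mean binocular ONSD was calculated", so eyes and repeats are averaged. Also, "Ultrasound was performed individually in both sagittal and transverse planes"; the text does not say whether the planes are pooled or tested separately.
- **Sonographers.** There are two, and their agreement is handled by correlation: "The inter-rater reliability of the sonographers for all time points were reported as interclass correlation values and 95% CI".

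The documents state no family-wise alpha, no sidedness and no count or list of post-hoc comparisons. The only indirect pointer to a 5% level is the use of 95% confidence intervals.

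**The concern.** A Bonferroni cutoff is the family-wise alpha divided by the number of tests. With both inputs missing, a reader has to recover them from the design, and the design points to three pairwise comparisons of time points. That gives a cutoff about ten times larger than the one printed.

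This is the only numerical decision threshold in the plan. If the groups are the time points, it decides which of them are declared different, and so whether a change in ONSD after collar placement is called significant. If 0.0016 was really applied to three tests, a true collar effect could be labelled non-significant by a rule that the design does not call for. If 0.016 was applied and the text is misprinted, the analysis is nearly right, but a reader using the printed rule would relabel any p-value from 0.0016 up to 0.016. The omnibus ANOVA is not affected in either case.

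**Working it through.** **Inputs**

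- Printed cutoff: 0.0016 (statistical paragraph).
- Time points: 3, namely baseline, 5 minutes and 20 minutes (Study Protocol). Pairwise comparisons: 3 × 2 / 2 = 3. That these form the post-hoc family is an inference.
- Family-wise alpha: not stated; 5% is assumed.

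**Step 1: try to reproduce 0.0016.** Cutoff = alpha / m, where m is the number of tests. At alpha = 0.05:

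| Family | m | 0.05 / m |
|---|---|---|
| Each post-collar time against baseline | 2 | 0.0250 |
| All pairs of time points | 3 | 0.0167 |
| Three pairs for each of two sonographers | 6 | 0.0083 |
| The same, in each of two planes | 12 | 0.0042 |
| All pairs of six sonographer-by-time cells | 15 | 0.0033 |

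None gives 0.0016. The Šidák version for three tests, 1 − 0.95^(1/3) = 0.0170, does not either.

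**Step 2: solve for m.** 0.05 / 0.0016 = 31.25. The values near it are:

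- m = 30: 0.001667, which gives 0.0016 only by truncation
- m = 31: 0.001613, by truncation or rounding
- m = 32: 0.001563, by rounding

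At other levels, 0.0016 needs:

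- alpha 2.5%: m = 15 (0.001667, truncated) or m = 16 (0.001563, rounded)
- alpha 1%: m = 6 (0.001667, truncated)
- alpha 0.5%: m = 3 (0.001667, truncated)

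**Step 3: can the design supply such a family?** Some routes can be constructed:

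- 15 pairs of sonographer-by-time cells × 2 planes = 30 tests at 5%.
- 2 contrasts × 2 sonographers × 2 eyes × 2 planes × 2 repeats = 32 tests at 5%.
- 15 pairs of sonographer-by-time cells at 2.5%.

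None is described. The 32-test route conflicts with averaging the eyes and repeats. The routes built on sonographer-by-time pairs include t-tests between sonographers, whereas the plan compares them by correlation.

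**Step 4: size of the discrepancy**

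- Three tests at 5%: 0.0167 / 0.0016 = 10.4 times stricter. Family-wise error is at most 3 × 0.0016 = 0.0048.
- Two tests against baseline: 0.025 / 0.0016 = 15.6 times stricter.
- Thirty tests: 0.001667 / 0.0016 = 1.04 times stricter. Family-wise error is at most 30 × 0.0016 = 0.048.
- The direction turns between 31 and 32 tests: 31 × 0.0016 = 0.0496 and 32 × 0.0016 = 0.0512.
- If 0.016 was applied to three tests: at most 3 × 0.016 = 0.048, and only p-values from 0.016 up to 0.0167 would change label.

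**Step 5: cost in power for three tests.** The two-sided normal critical values are 2.394 at 0.0167 and 3.156 at 0.0016, and 80% power adds 0.842. A contrast with 80% power at 0.0167 therefore has power Φ(2.394 + 0.842 − 3.156) = Φ(0.080), about 53%, at 0.0016.

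**The case against.** The strongest reply is that this is under-specification, not a demonstrated arithmetic error. Alpha and m are both absent, 0.0167 rests on an assumed 5% and an inferred three tests, and families that give 0.0016 can be constructed. The three-test family is also not fully secure. The text averages eyes and repeats, but it does not say that planes and sonographers are pooled, and reporting a correlation does not rule out separate t-tests for each sonographer. The statistical paragraph also uses a chi-squared test to compare proportions among groups. Recorded categorical items such as trauma etiology do not change between baseline and 20 minutes, so *groups* may include patient subgroups, and m could then exceed three. Finally, on the three-test reading the cutoff is conservative: it costs power and does not inflate false positives.

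Much of this is fair. The value 0.0016 is not shown to be impossible for every conceivable family. The misprint explanation is conjecture, since it needs 0.0167 to be truncated to 0.016 and then given an extra zero. The objection does not make the number traceable, however. Splitting by sonographer and plane gives 12 tests and 0.0042, still not 0.0016. No subgroup family is described either, and if one was meant, the case for listing the comparisons is stronger. Conservatism is no defence of a cutoff that does not fit its comparisons, because the lost power falls on the collar effect that the study sets out to measure.

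**Conclusion.** The concern holds. The printed cutoff cannot be derived from the comparisons that the documents describe, and neither of its two inputs is stated. If the family is three time-point comparisons at 5%, the cutoff should be 0.0167. The printed value is then about ten times too strict, and results with p from 0.0016 up to 0.0167 would be mislabelled as non-significant. The size and direction depend on the two assumptions, alpha of 5% and m = 3: at 5% the printed value is strict for up to 31 tests and slightly lenient at 32.

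Confidence is high that 0.0016 is not traceable to the described design. A slip from 0.016 is a plausible explanation that the documents cannot confirm. They also do not show which cutoff was applied or whether any p-value lies in the affected range. The point should be fixed, but it does not undermine the omnibus analysis.

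**What to change.** 1. State the family-wise alpha and its sidedness, define *groups*, and list the post-hoc comparisons as originally intended, without reference to the results.
2. Set the cutoff to match. At 5% that is 0.0167 for all three pairs of time points, or 0.025 for the two comparisons against baseline. If 0.0016 was intended, give the comparisons and the level that produce it.
3. Confirm which cutoff was actually applied. If it was 0.016, correct the text and check only p-values from 0.016 up to 0.0167. If 0.0016 was applied without a supporting family, re-judge the existing post-hoc p-values against the matched cutoff.
4. Disclose any correction. A looser cutoff can only add significant results, so the reader needs to see that the comparisons were not chosen to suit them.

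The cost is one or two sentences and, at most, a relabelling of existing p-values. No new data or new tests are needed.

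### Is it a flaw that sonographer agreement is planned for ONSD at each time point and not for the change from baseline?

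*Combined protocol and SAP*

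**What the plan says.** The Study Protocol section has two sonographers measure ONSD. At baseline, "Each eyes measurements were recorded for two times and then a mean binocular ONSD was calculated". After the collar is fitted, "The same technique used to measure the ONSD after c-collar placement and the mean ONSD was again calculated", and "This process was done at time points after placement of c-collar; 5 minutes and 20 minutes". There are thus three time points, and the recorded quantity at each is a mean ONSD. The sonographers work independently: "Both physicians were blinded to each other measurements".

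On earlier reliability the section gives one figure: "The intraclass correlation coefficient of the two sonographers for sonographic measurement of ONSD was >0.9 according to local annual quality checks". It does not state the form of the coefficient, the number of readings or a confidence interval.

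The unheaded statistical paragraph at the end plans the comparison: "The significance of the difference between groups was assessed by ANOVA test", with Student's t-tests post hoc. Its last sentence plans the agreement analysis: "The inter-rater reliability of the sonographers for all time points were reported as interclass correlation values and 95% CI". Neither place defines a change score as an outcome, and neither plans a statement about individual patients.

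**The concern.** The title asks what a collar does to ONSD, and the design answers by measuring the same patients before and after. The natural measure of effect is a within-patient change, yet reliability is planned only for the level at each time point. A coefficient of levels is dominated by stable differences between patients, and these drop out of a change. Two sonographers could correlate at 0.90 at every time point and still disagree badly on who changed and by how much.

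Two details add to the unease. The statistical paragraph says interclass where the Study Protocol section says intraclass for the same two sonographers. If an ordinary correlation were meant, a constant difference between them would not show. Nor is a mean difference or limits of agreement planned. At stake would be a high coefficient being taken as proof that a collar-related change is reproducible between observers.

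**Working it through.** **Inputs.** The only reliability figure in the documents is the coefficient above 0.9 from local quality checks. It cannot be reproduced, because no data, sample size or form are given. Everything else below is assumed. Work in units of the between-patient SD of one reading, with

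- R = level reliability, so error variance 1 − R per sonographer;
- c = correlation of one sonographer's error between two time points;
- r = correlation of one sonographer's baseline and follow-up readings;
- d = constant offset between the sonographers.

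**Step 1: does a level coefficient fix agreement on change?** The difference between the two sonographers' changes has variance 4(1 − R)(1 − c), so the 95% limits are ±1.96√[4(1 − R)(1 − c)]. Reliability of change is [R − r + (1 − R)c]/(1 − r). With r = 0.8:

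| R | c | limits for change (SD) | reliability of change |
|---|---|---|---|
| 0.90 | 0 | ±1.24 | 0.10/0.20 = 0.50 |
| 0.90 | 0.5 | ±0.88 | 0.15/0.20 = 0.75 |
| 0.90 | 0.8 | ±0.55 | 0.18/0.20 = 0.90 |
| 0.95 | 0 | ±0.88 | 0.15/0.20 = 0.75 |
| 0.95 | 0.5 | ±0.62 | 0.175/0.20 = 0.88 |
| 0.95 | 0.8 | ±0.39 | 0.19/0.20 = 0.95 |

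Over r = 0.7 to 0.85 and c = 0 to 0.8, the extremes are (0.90 − 0.85)/0.15 = 0.33 (R = 0.90, c = 0) and (0.95 − 0.70 + 0.04)/0.30 = 0.97 (R = 0.95, c = 0.8). So it does not. The premise of the concern is correct, but the result is compatible with good agreement as well as poor.

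**Step 2: does this reach the collar effect?** If the second sonographer reads d higher throughout, that sonographer's change is (follow-up + d) − (baseline + d) = follow-up − baseline. The offset vanishes whatever its size. Random disagreement has mean zero; it adds to the spread of the ONSD values entering the ANOVA and t-tests, and so is already reflected in their standard errors.

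**Step 3: would the form of the coefficient matter?** An absolute-agreement ICC equals R/(1 + d²/2). With R = 0.95 and d = 0.3 it is 0.95/1.045 = 0.91; with R = 0.90 and d = 0.5 it is 0.90/1.125 = 0.80. A consistency ICC stays at 0.95 or 0.90. The form therefore affects how an offset shows in the level report. By step 2 the same offset drops out of the change.

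**Step 4: what do the planned outputs already give?** SDs and a coefficient at each time point are to be reported. If the coefficient is an intraclass one, SD × √(1 − ICC) is the measurement error of a reading: √0.10 = 0.32 SD at 0.90. Even with perfectly negative error correlation (c = −1), the limits for change cannot exceed 1.96√(4 × 0.10 × 2) = ±1.75 SD; with c at or above zero they are at most ±1.24 SD. These bounds are wide, but they exist without further analysis.

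**Step 5: would an ICC of the change be a better guide?** Keep R = 0.90 and c = 0, so that measurement error is fixed and the limits stay at ±1.24 SD. Then r is R times the correlation of patients' true ONSD over time. If that true correlation is 0.5, r = 0.45 and the ICC of change is 0.45/0.55 = 0.82. If it is 0.99, r = 0.891 and the ICC is 0.009/0.109 = 0.08. The coefficient collapses merely because patients change by nearly the same amount. Under a uniform collar effect it would suggest poor agreement although the sonographers measure exactly as well as before.

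**The case for a change.** The strongest case for the concern is that the design plainly aims at change, even though the text never defines it as an outcome. Reporting agreement at every time point implies that paired readings from both sonographers exist, so limits of agreement for the 5- and 20-minute changes would need no new data. Without them a reader may over-interpret a high level coefficient. Correcting interclass to intraclass would not help, since no coefficient of levels carries the missing information.

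Most of this is factually right. The reports as planned will not show agreement on change, the form of the coefficient is not stated, and the two spellings differ. What does not follow is that something planned goes wrong. The plan makes no claim about reproducibility of change or about a single patient, so no stated conclusion rests on the missing analysis. The different spelling is most likely a slip, as both sentences concern the reliability of the same two sonographers. Guarding against a possible over-reading is a reasonable wish, but a matter of preference in secondary reporting. One natural form of that addition, an ICC of the changes, could mislead by itself, as step 5 shows.

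**Conclusion.** The concern does not hold. Coefficients with 95% confidence intervals at all time points describe the reliability of the quantity the plan records and compares, mean ONSD at each time. Followed as written, and read as intraclass, the sentence gives a sound level-reliability result and leaves the mean collar effect unbiased: a constant offset between sonographers contributes zero to it.

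The range of 0.33 to 0.97 for reliability of change rests entirely on assumed correlations and on level coefficients of 0.90 and 0.95, the first of which is the boundary that the stated figure exceeds. It measures what is unknown and does not demonstrate a deficiency.

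The conclusion rests on three assumptions: interclass is a slip for intraclass; each sonographer measures at all three time points, as the planned agreement analysis implies; and any difference between them is constant over time. It would need another look if the report went on to claim that individual changes are reproducible between observers. The plan makes no such claim.
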